2.5 Trial Assessments

Primary outcome:

Total opioid consumption over 48 hours. This will be converted to oral morphine equivalents as per the methods prescribed by the Faculty of Pain Medicine of the Australian and New Zealand College of Anaesthetists.

(<http://fpm.anzca.edu.au/documents/opioid-dose-equivalence.pdf>)

Secondary outcomes:

- Quality of Recovery (QoR-15) scores collected 24 and 48 hours after commencement of the study infusion.
- Time to first assisted mobilisation measured in minutes after discharge from PACU.
- Passive range-of-movement on day 1 and day 2, 24 and 48 hours after commencing the study infusion.
- Number of doses of antiemetic required over the 48-hour study period.
- Hospital length of stay measured in days.
- Side effects including nausea and vomiting, pruritis and sedation (Pasero opioid-induced sedation scale) collected daily.
- “Timed up and go” or TUG test 24, 48 and 72 hours after commencement of study infusion; TUG test is the time in seconds it takes the patient to stand from the chair, walk 3 meters, turn around and sit down again.
- Passive range-of-motion; the range of knee flexion will be recorded by the research nurse using a goniometer at the same follow up time intervals.

Post-operative Analgesia:

- Regular paracetamol (1gram Q6h) and celecoxib (100mg BD) unless contraindications exist.
- Do not prescribe sustained release opioid preparations (OxyContin or M-Eslon)
- Avoid prescribing IV Morphine and Patient Controlled IV Analgesia, unless strong reasons exist (e.g. Chronic pain states or pre-existing therapy).
- Patient will have access to the following PRN analgesia if required.

- Sevredol: Morphine immediate release 10-20mg PO Q2 hours PRN
- Tramadol 50-100mg either PO or IV Q6 hours PRN
- Oxycodone Immediate release (OxyNorm): 5-10mg PO Q2 hours PRN

A trial safety and data adjudication committee with three members independent from the study will be established to adjudicate serious adverse events and determine the need to stop the administration of trial drugs. Given the established safety of the medicine and technique, it is anticipated that this should be infrequent.

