2.3 Suggested Perioperative Pro Forma

1. **Starvation / Nil by mouth status:** as per current anaesthetic department guidelines; 6 hours for solid food, 4 hours for free oral fluids, and 2 hours for clear oral fluids.
2. **Premedication:** Paracetamol 1 gram or 20mg/kg in patients less than 50kg.
3. **Primary anaesthetic technique:** spinal anaesthesia with either isobaric or heavy bupivacaine 0.5% to a maximum of 3ml (15mg). No additives (e.g. intrathecal morphine or fentanyl) are permitted.
4. **Sedation:** Midazolam 1-2mg may be used to help facilitate spinal anaesthetic placement. During surgery, Propofol either by constant infusion or target controlled infusion (TCI) may be used for patient satisfaction and safety.
5. **General Anaesthesia:** While it is suggested that general anaesthesia is avoided, this may be required in the event of the crisis or at the request of the patient and/or

the anaesthetist. If general anaesthesia is to be used, we suggest Propofol TCI as the primary agent.

6. **Rescue analgesia**: fentanyl boluses of 25-50mcg every 5 minutes can be used in conjunction with the sedation technique described above in the event of patient discomfort. This should be recorded on the patient chart and the reason for the administration noted on the study case reporting form (CRF).
7. **Local Infiltrative analgesia (LIA)**: Ropivacaine 0.2% (2mg/ml) 150mls (total 300mg) with adrenaline 5mcg/ml (total 750mcg) should be injected prior to implantation of the prostheses. The technique of injection should be methodical and follow the current standard of practice at Counties Manukau Health.
8. **Supplementary agents**: in patients where nonsteroidal anti-inflammatory drug (NSAID) use is not contraindicated, parecoxib 40mg should be given intraoperatively. This should be followed by celecoxib 100mg BD for the duration of hospitalization.
9. **Antiemetic Therapy**: Dexamethasone (4-8mg) and Ondansetron (4mg) should be administered as antiemetic therapy if not contraindicated.
10. **Intravenous fluid therapy**: at the discretion of the treating anaesthetist. In routine patients without haemorrhage, 1000-2000ml of balanced crystalloid solution is suggested.

In addition to these guidelines, the use of indwelling bladder catheter and tranexamic acid use is at the discretion of the treating surgeon and anaesthetist. Patient mobilisation should take place on the day of surgery and will be assisted by the ward based nursing and allied health staff.

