2.4 Placement of the Adductor Canal Catheter

At the end of surgery after sterile surgical dressing have been applied, an ultrasound guided adductor canal catheter will be placed on the operative limb using an aseptic technique. A multiorifice catheter (e.g. Contiplex or Contiplex C *B.Braun AG, Melsungun, Germany*) should be placed either within the distal femoral triangle or within the adductor canal deep to the Sartorius muscle. At least 2cm catheter should be left beyond the end of the needle. The catheter can be secured with both tissue glue and/or a catheter anchoring device prior to the administration of a sterile dressing.

No local anaesthetic will be administered down the catheter until the attachment of the prescribed infusion in the post-anaesthesia care unit (PACU). Randomisation will have taken place using opaque envelopes. Both the participants and the research nurses will not be aware which treatment a particular patient is receiving whereas the PACU nurses involved in the programming of the infusion pump and attaching the infusion to the patient will not be blinded. Participants will be randomised to receive either:

1. Continuous infusion group – 5 mls/hr of ropivacaine 0.2% for 48 hours
2. Programmed intermittent bolus group – 10mls ropivacaine 0.2% every two hours for 48 hours.

The time of infusion commencement will be noted down and the trial will run for 48 hours from this point. During this trial period, the assessments will take place at specified time points; 24 hours, 48 hours and 72 hours after the commencement of the infusion.

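### The mobilisation clock starts at PACU discharge, after the allocated infusion has begun, so any between-arm difference in PACU stay shifts the comparison by the same amount.

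*Protocol*

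**What the plan says.** Section 2.5 of the protocol lists among the secondary outcomes "Time to first assisted mobilisation measured in minutes after discharge from PACU".

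Section 2.4 fixes what happens before that point. On allocation it says: "Randomisation will have taken place using opaque envelopes". The catheter carries no drug until the prescribed infusion is attached in PACU. On blinding, "the PACU nurses involved in the programming of the infusion pump and attaching the infusion to the patient will not be blinded". On the trial clock, "The time of infusion commencement will be noted down and the trial will run for 48 hours from this point".

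Other timed outcomes use that clock. Section 2.5 has "Quality of Recovery (QoR-15) scores collected 24 and 48 hours after commencement of the study infusion", and it ties range of movement and the timed up-and-go test to the same starting point.

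Section 2.3 describes the setting: "Patient mobilisation should take place on the day of surgery and will be assisted by the ward based nursing and allied health staff".

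**The concern.** The protocol fixes the order as randomise, start the allocated infusion in PACU, leave PACU, mobilise. The outcome's time origin is therefore an event after treatment start. In principle it can be affected by the treatment, through early pain, opioid use or sedation, or by unblinded PACU staff. Randomisation makes the arms comparable at allocation; it does not make them comparable at PACU discharge.

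At stake is the meaning of the mobilisation comparison. If the arms leave PACU at different times, the outcome no longer measures how soon patients mobilise after treatment begins. A gain made inside PACU is charged against the arm that made it. Section 2.6 names mobilisation among the benefits that, if seen, would have economic effects, so a distorted result could be carried into that argument. The primary outcome, 48-hour opioid consumption, is not touched.

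**Working it through.** The protocol states no figure on this point, so there is none to reproduce.

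**Identity.** For each patient let M be the time from infusion start to first assisted mobilisation, P the time from infusion start to PACU discharge, and R the time recorded under the protocol's definition:

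R = M − P

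Taking differences between arms (the arm that leaves PACU sooner minus the other):

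ΔR = ΔM − ΔP

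This is exact. The recorded comparison equals the one from infusion start only if ΔP = 0.

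**Illustration.** Assume that one arm leaves PACU 30 minutes sooner, ΔP = −30. The protocol gives no such figure.

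| ΔM, from infusion start (min) | ΔR = ΔM + 30 (min) | What the protocol's outcome shows |
|---|---|---|
| 0 | +30 | a delay where there is no difference |
| −15 | +15 | benefit reversed |
| −30 | 0 | benefit erased |
| −60 | −30 | benefit halved |

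With infusion commencement as the origin, the comparison is the first column, whatever happens to PACU stay.

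**Scale against sampling error.** Suppose there is no true difference in M, and PACU stay differs by s minutes. The approximate chance of a significant result in the direction of a false delay, at the two-sided 0.05 level of Section 3, is

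Φ( s / (SD × √(2/n)) − 1.96 )

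with n per arm. The sample size is not yet fixed. Section 1.4 says similar trials enrolled 40 to 60 patients, so n = 20 and n = 30 are used for illustration. The SDs and values of s are assumptions.

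Example: n = 20, SD = 120, s = 30. The standard error is 120 × √(2/20) = 37.9; 30/37.9 = 0.79; Φ(0.79 − 1.96) = Φ(−1.17) = 12%.

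| n per arm | SD (min) | s = 15 | s = 30 | s = 60 |
|---|---|---|---|---|
| 20 | 120 | 6% | 12% | 35% |
| 20 | 60 | 12% | 35% | 89% |
| 30 | 120 | 7% | 16% | 49% |
| 30 | 60 | 16% | 49% | 97% |

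The nominal rate in that direction is 2.5%. These figures show how the bias grows if PACU stay differs. They are not estimates of what will happen in this trial.

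**The case against.** **PACU stay may hardly differ.** Both arms receive the same average volume (5 ml/h × 2 h = 10 ml per two hours). The pro forma in Section 2.3 suggests the same spinal anaesthetic and the same 300 mg ropivacaine infiltration for everyone. Section 1.2 presents the catheter as a way to prolong analgesia as the infiltration wanes. A difference between delivery modes while the patient is still in PACU is thus conjecture. This stands, and it limits the likely size of the bias. It does not rule the bias out, because the arms differ in delivery from attachment onwards and the PACU nurses who attach the infusion know the allocation.

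**The origin has a practical reason.** Ward staff assist mobilisation, so PACU discharge marks when it normally becomes possible, and counting from infusion start adds PACU waiting time. This also stands as a real cost. But the ward interval answers a different question, and its convenience does not make PACU discharge a starting point protected by randomisation.

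**Infusion commencement also follows randomisation and is in the hands of unblinded nurses.** True, but it precedes any effect of the study drug, which PACU discharge does not.

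**Stronger readings that the protocol does not support.**

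- A reader might infer that any treatment that shortens PACU stay will be scored as delaying mobilisation. That holds only if mobilisation after infusion start improves by less than PACU stay shortens.
- A reader might take this outcome as the only one not anchored to infusion start. It is not: side effects are collected daily, and length of stay has no stated origin.
- A reader might extend the criticism to "Hospital length of stay measured in days" as too coarse. The text does not say whole days, nor that both arms stay about 48 hours, so that criticism lacks a basis.
- A reader might fault the lack of a time-to-event method. That is commonly left to the statistical analysis plan, which is not shown.

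**Conclusion.** The point holds for the time origin of this one secondary outcome. PACU discharge comes after randomisation and after the start of treatment, and the between-arm comparison is shifted by exactly the difference in PACU stay, against the arm that leaves sooner. A benefit is understated, erased or reversed depending on whether mobilisation improves by more than, as much as, or less than PACU stay shortens.

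The direction and form of the shift follow from the protocol alone. Its size does not: there are no PACU-stay data in the protocol and nothing to show that stay will differ by arm, so the bias is unknown and may be small. Every minute figure and SD in the illustrations is assumed. The change is worth making because it removes a possible bias at almost no cost, not because a large bias has been shown.

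**What to change.** In Section 2.5, define the outcome as minutes from commencement of the study infusion to first assisted mobilisation. If PACU stay is of interest, report it separately as minutes from infusion commencement to PACU discharge, so that a reader can see whether it differs by arm.

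The cost is wording. Section 2.4 already has the infusion start time noted, and the times of mobilisation and PACU discharge are both needed to compute the outcome as now defined. The one downside is that time spent waiting in PACU is then included in the outcome; reporting PACU stay alongside makes that visible.

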1.2 Background

Total knee arthroplasty (TKA) is offered to patients with significant disorders of the knee arising from ageing, degenerative disease or after trauma. With the ageing population, this procedure will become more frequent and consume increasing amounts of health care resources (1). Current guidelines for TKA patients place an emphasis on early mobilisation and discharge to back to the community for home-based rehabilitation (2).

Despite the potential for considerable functional improvement after surgery, TKA is a painful procedure (4). The perioperative analgesic management is one area in which the anaesthetist can influence patient satisfaction and early joint function. To facilitate early mobilisation and rapid discharge, there has been a shift away from traditional techniques that produce systemic side effects or motor weakness - both which hamper post-operative rehabilitation efforts (2,5).

At Counties Manukau Health, the use of high-volume infiltration of low concentration local anaesthesia (LIA) has become the cornerstone of pain management following TKA. This technique is supplemented with multimodal oral analgesia and/or peripheral nerve catheters. A recent study conducted at Counties Manukau confirmed the relative safety of LIA with no observations of toxicity after recording peak local anaesthesia levels between six and twenty-four hours after surgery indicating that there is capacity for additional local anaesthetic use in the perioperative period (6).

As the levels of local anaesthetic begin to fall, evidence from randomized controlled trials and metaanalyses suggest analgesic efficacy of LIA begins to wane (7). To prolong the duration of effective non-opioid analgesia, the anaesthetist can place a

peripheral nerve catheter under ultrasound guidance near the nerves supplying sensation to the operative knee. One such example is the adductor canal catheter (ACC) which provides ongoing pain relief by using local anaesthesia to dampen pain signals generated from the operative site (8,9). The ACC prolongs analgesia without significant motor blockade; patients are less reliant on opioid analgesia and are able to participate in rehabilitation. Evidence from randomised controlled trials suggests that the ACC is a safe intervention which is complementary, and may enhance, the effect of LIA (10).

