Post-operative use of an ACC after TKA was first trialled at Counties-Manukau Health in 2015 and it has increasingly been utilised by anaesthetists to achieve the goals as outlined above. In 2018, the Department of Anaesthesia and Pain Medicine enrolled patients in an international trial to determine the most effective site of catheter insertion, the results of which are yet to be published.

There is considerable debate as to what constitutes the most effective method of local anaesthetic administration through peripheral nerve catheters (11). Two potential options include the continuous administration of a fixed amount of local anaesthetic each hour or the use of a programmed intermittent bolus (PIB) whereby a bolus of local anaesthetic is provided every one to two hours through the catheter. PIB may result in greater spread of local anaesthetic which may lead to improved analgesic outcomes (12). Our department has recently completed a meta-analysis which concluded that PIB may be more efficacious, especially for lower limb catheters, than continuous local anaesthetic administration. The benefits seen included a reduction in total local anaesthetic and opioid consumption with no deleterious effect on patient satisfaction or side effects (article submitted for publication).

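### The side effects named are all opioid-type: no harm specific to local anaesthetic delivery is prespecified, and motor effect is seen only indirectly

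*Protocol*

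**What the plan says.** Protocol section 2.5 gives the side-effect outcome as "Side effects including nausea and vomiting, pruritis and sedation (Pasero opioid-induced sedation scale) collected daily". The other secondary outcomes closest to motor function are "TUG test 24, 48 and 72 hours after commencement of study infusion" and "Time to first assisted mobilisation measured in minutes after discharge from PACU". Range of movement is also recorded, but passively.

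Section 2.5 sets up a three-member independent committee "to adjudicate serious adverse events and determine the need to stop the administration of trial drugs". It adds: "Given the established safety of the medicine and technique, it is anticipated that this should be infrequent".

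Section 1.2 gives the reasoning behind the comparison:
- On mechanism: "PIB may result in greater spread of local anaesthetic which may lead to improved analgesic outcomes".
- On motor effect: "The ACC prolongs analgesia without significant motor blockade". The same section names motor weakness among the reasons that practice moved away from older techniques.
- On toxicity, it reports a local study of infiltration with "no observations of toxicity after recording peak local anaesthesia levels between six and twenty-four hours after surgery". It then cites randomised evidence that the catheter is safe and complements infiltration.

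The synopsis and sections 1.1, 2.1 and 2.4 state that the arms receive the same care apart from the mode of ropivacaine delivery. Sections 2.1 and 2.4 keep the research nurse unaware of allocation.

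**The concern.** The harms that the randomised difference could change directly are those of local anaesthetic delivery: toxicity symptoms, leg weakness with its consequences (buckling, falls), and failure of the catheter or infusion. Nausea, itch and sedation can change only at one remove, through opioid use, which is already the primary outcome. The named list therefore follows the primary outcome and leaves out the harms closest to the intervention.

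The protocol intends its result to change care pathways locally and to influence practice elsewhere (sections 1.3, 2.6 and 6). A reader of the report would expect at least a count, by arm, of intervention-specific harms. Which outcomes are collected is settled in the protocol and case report form before the first patient. A later analysis plan cannot restore events that nobody asked about.

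**Working it through.** The protocol states no event rate, safety margin or sample size, so there is no figure to reproduce. The check has three parts.

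**1. Which harms have a stated route to being recorded (section 2.5)**

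| Harm | Named outcome | Indirect or other route |
|---|---|---|
| Nausea and vomiting, pruritus, sedation | Yes, daily | Antiemetic doses |
| Toxicity symptoms, non-serious | None | None stated |
| Leg weakness | None | TUG, time to mobilisation |
| Fall or buckling, non-serious | None | None stated |
| Catheter dislodgement or leak | None | None stated |
| Early cessation of infusion | None | None stated, unless stopped by the committee |
| Any of these, if serious | – | Committee adjudication |

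**2. What differs between the arms (section 2.4; 0.2% = 2 mg/mL)**
- Continuous: 5 mL/h × 2 mg/mL = 10 mg/h; 10 × 48 = 480 mg.
- Intermittent bolus: 10 mL × 2 mg/mL = 20 mg per bolus; 48/2 = 24 boluses; 24 × 20 = 480 mg. If boluses fall at both 0 and 48 h, 25 × 20 = 500 mg.

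The planned total is essentially equal. The contrast is the delivery pattern, so the relevant harms are those of spread and of delivery.

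**3. What recording could and could not show**

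Section 1.4 leaves the size open and says that similar trials enrolled 40 to 60. With 1:1 allocation this is n = 20 to 30 per arm, taken here as an assumption. All event rates below are also assumptions.

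- One-sided 95% upper bound after zero events, 1 − 0.05^(1/n): 13.9% at n = 20 and 9.5% at n = 30. The upper limit of the two-sided 95% exact interval, 1 − 0.025^(1/n), is 16.8% and 11.6%.
- Chance of at least one event in an arm, 1 − (1 − p)^n: 18% to 26% if p = 1%; 33% to 45% if p = 2%; 64% to 79% if p = 5%.
- Power of the two-sided Fisher exact test at 0.05, summing binomial probabilities over all tables with p ≤ 0.05: for 2% versus 10%, 2.9% (n = 20) and 4.3% (n = 30); for 5% versus 15%, 7.0% and 9.3%.
- Number per arm for 80% power, [1.96√(2p̄(1 − p̄)) + 0.842√(p₁(1 − p₁) + p₂(1 − p₂))]² / (p₁ − p₂)², where p̄ is the mean of p₁ and p₂: 138 for 2% versus 10%, and 141 for 5% versus 15%.

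Recording would therefore support description with wide intervals, and no comparative safety conclusion.

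**The case against.** Several points on the other side stand.

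- The list is open: the text says that side effects include those named, and the case report form mentioned in section 2.3 is not shown and may hold more. But an unnamed item carries no commitment to ask every patient. Section 2.2 promises to collect deviations from the perioperative pro forma, but that pro forma does not cover the catheter infusion.
- TUG and time to mobilisation do reflect weakness, so it would be wrong to infer that a difference between arms must go unseen. They mix weakness with pain, however, and do not count falls or buckling. The protocol does not say how inability to attempt TUG is recorded. That is commonly left to the case report form or analysis plan, so missing TUG values in weak patients are a possibility and not an established defect.
- Serious toxicity or an injurious fall could reach the committee. A reader might infer that only spontaneously reported events would do so, but the protocol does not say how serious events are found.
- A reader might infer that the safety rationale rests on infiltration alone and ignores the combination with a catheter. Section 1.2 does not support this: it also cites randomised evidence on the catheter as a complement to infiltration.
- A reader might see a dose concern in the ropivacaine total. That total is essentially common to both arms, and the protocol gives no threshold against which to judge it, so it says nothing about a difference between arms.

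The strongest objection is that the trial does not set out to demonstrate equal safety. That is correct, and it limits the point to ascertainment and to how the result is worded.

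**Conclusion.** The point holds as a gap in prespecified harms. All named side effects are opioid-type, no harm specific to local anaesthetic delivery is named, and motor effect is captured only through functional tests. This sits badly with the protocol's own account of what differs between the arms and of the concerns that matter.

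It is tempting to conclude that the trial therefore cannot show the preferred technique to be as safe. The document does not support putting it that way. No equivalence or non-inferiority aim or margin is stated, and at 20 to 30 per arm the limitation comes mainly from size. It would remain after the fix, with an upper bound of about 10% to 14% after zero events and Fisher power of about 3% to 9% at the assumed rates. These figures rest on the size of similar trials, because this trial's own size is not yet set.

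The gain is a systematic record of harms by arm. It is a worthwhile, inexpensive improvement and does not threaten the validity of the primary comparison.

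**What to change.** Add to section 2.5, and to the case report form, a short yes/no record completed by the blinded research nurse at the existing 24, 48 and 72 hour assessments:

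1. symptoms suggestive of local anaesthetic toxicity;
2. leg weakness, including inability to attempt TUG because of weakness;
3. any fall or knee buckling;
4. catheter dislodgement or leak;
5. early cessation of the infusion, with the reason.

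Report counts by arm descriptively with exact confidence intervals, and supply them to the safety committee. State in the protocol that any superiority conclusion concerns efficacy only.

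The cost is slightly longer visits, with no new visit or procedure. The counts will be too small for a comparative safety conclusion, and the report should say so.

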1.4 Number of Patients

The study size will depend on the power calculation. This information is yet to be collected. Similar trials testing for differences in effect between continuous and intermittent bolus techniques have enrolled between 40 to 60 patients. Once the clinically significant treatment effect has been determined, we will calculate the sample size using standard techniques with $\alpha = 0.05$ and $\beta = 0.2$

2. Research Methods

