2.6 Benefits to Participants

Potential benefits to participants include helping healthcare providers determine the most efficacious mode of local anaesthetic administration through an ACC. This may lead to changes in care pathways at Counties-Manukau Health and could have considerable benefits for future patients undergoing TKA. Depending on the individual's mindset, the participation in clinical research can lead to considerable satisfaction. As there is no control or placebo group, active therapeutic interventions will not be withheld, participants are not at risk of missing out on the therapeutic benefit of an ACC.

For both the District Health Board and the wider anaesthetic community, the results of this study could provide some clarification to changes which may be required in our pathways for patient care after TKA. Should benefits be seen in mobilisation, satisfaction or hospital length of stay, there are obvious economic effects including the reduction in overall healthcare costs and improved compliance with rehabilitation protocols.

3. Statistical Considerations

The statistical assessment of trial data will be devised and performed by a biostatistician. Patient demographic, surgical and anaesthetic factors will be recorded and tabulated. Demographic data will be presented as number (percentage) for discrete observation and mean (standard deviation) for continuous parameters.

For primary outcome (analgesic consumption in oral morphine equivalents) a test for differences in means / variances will be performed as guided by the data. Statistical test will be two-tailed with $p=0.05$ used as the threshold for statistical significance. Where possible, the clinical relevance of a statistical test will be provided in addition to the p-value. Similar testing strategies will be used for the secondary outcomes with differences in discrete observations (e.g. yes/no data) determined using the Fisher Exact test.

4. Data collection and retention

Data collection will be performed primarily by a research nurse specialist and/or investigator who will visit postoperatively to obtain the necessary parameters on paper form – this will be stored inside a secure cabinet in the department of anaesthesia and pain medicine. A Microsoft Excel spread sheet will be designed with various worksheets for data collection and analysis – this will be password protected and only accessed by approved investigators from within the Counties Manukau Health network.

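### Timed up-and-go in seconds gives no value for patients unable to do the test, and no provision is described for those discharged before 72 hours; comparing completers is probably biased toward no difference

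*Protocol*

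**What the plan says.** Protocol section 2.5 lists the timed up-and-go (TUG) as a secondary outcome: "TUG test 24, 48 and 72 hours after commencement of study infusion". The only definition is that the "TUG test is the time in seconds it takes the patient to stand from the chair, walk 3 meters, turn around and sit down again". There is no category for a test that was attempted and failed, or not attempted. Section 2.5 also has knee flexion measured at the same follow-up times, and section 2.4 names those times as 24, 48 and 72 hours.

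Section 3 says that for the primary outcome "a test for differences in means / variances will be performed as guided by the data", and that "Similar testing strategies will be used for the secondary outcomes", with Fisher's exact test for discrete data.

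Three further facts bear on the 72-hour test. The infusion stops at 48 hours (section 2.4). Length of stay is itself a secondary outcome (section 2.5). Outcomes are collected at postoperative visits by a research nurse or investigator, with no mention of visits after discharge (section 4). The background in section 1.2 adds: "Current guidelines for TKA patients place an emphasis on early mobilisation and discharge".

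**The concern.** A time in seconds exists only for a patient who completes the walk. At 24 hours the patients without a time will include those with too much pain, weakness or dizziness to do it, and these are the poorest results. At 72 hours, a day after the infusion ends, some of the quickest to recover may have gone home. In both cases the gap in the data comes from the function being measured, arises after randomisation, and may differ by arm.

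A comparison of seconds among completers is then not a comparison of the randomised groups. If one arm gets more frail patients through the test, their slow times enter that arm's mean, while their counterparts in the other arm drop out. If one arm sends more strong patients home, it loses its best times. A 72-hour knee-flexion reading has the discharge problem too.

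**Working it through.** The protocol gives no TUG mean, SD, effect or missing rate, so there is no stated figure to reproduce. What follows shows the mechanism on assumed inputs.

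**Model.** TUG is log-normal with median M and log-SD s = 0.6. Intermittent bolus is 15% faster (ratio 0.85). With cut-off c, let k = ln(c/M)/s.
- Mean of all patients: M·exp(s²/2)
- Mean of completers if those above c are unable: M·exp(s²/2)·Φ(k−s)/Φ(k)
- Mean of completers if those below c are home: M·exp(s²/2)·Φ(s−k)/(1−Φ(k))

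**24 hours, c = 90 s**

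| | Continuous (M = 60) | Bolus (M = 51) | Gap |
|---|---|---|---|
| Mean, all patients | 71.8 s | 61.1 s | 10.8 s |
| Unable | 25% | 17% | |
| Mean, completers | 50.8 s | 46.9 s | 3.9 s |

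Loss = 1 − 3.9/10.8 = 64%. It is 48% with c = 120 s and 81% with c = 60 s.

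**72 hours, c = 30 s**

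| | Continuous (M = 35) | Bolus (M = 29.75) | Gap |
|---|---|---|---|
| Mean, all patients | 41.9 s | 35.6 s | 6.3 s |
| Gone home | 40% | 51% | |
| Mean, completers | 56.0 s | 51.9 s | 4.1 s |

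Loss = 1 − 4.1/6.3 = 35%. It is 30% with c = 25 s and 39% with c = 35 s.

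**How much rests on the sharp cut-off.** In these tables TUG alone decides who is missing. Keep the same cut-offs, but let a latent variable with correlation ρ to log-TUG decide instead (simulated):

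| ρ | Loss at 24 h | Loss at 72 h |
|---|---|---|
| 1 | 64% | 35% |
| 0.8 | 46% | 14% |
| 0.6 | 30% | about 1% |
| 0.3 | 12% | −6% (slight inflation) |

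With no link (ρ = 0) there is no bias.

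**Loss in one arm only.** In a second assumed model (continuous-arm median 40 s, log-SD 0.5, ratio exp(−0.20)), if only the bolus arm loses its slowest 20%, the gap grows to 1.94 times the truth. If only the continuous arm loses its fastest 20%, it grows to 1.76 times.

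**Does ranking help?** The protocol fixes no sample size but says that similar trials "have enrolled between 40 to 60 patients", so 30 per arm is the upper end. Simulated power at two-sided 0.05 in the second model, with ratio exp(−0.36) and the slowest patients unable:

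| Unable (both arms pooled) | t-test, all patients (unobservable) | t-test, completers | Rank-sum, unable worst |
|---|---|---|---|
| 10% | 0.73 | 0.57 | 0.74 |
| 30% | 0.72 | 0.34 | 0.72 |

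In the first model at 24 hours with ratio 0.70, power is about 0.34 for completers and 0.58 for ranks. With ratio 0.85 it is about 0.10 and 0.17, against 0.15 for the full data.

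**The case against.** **Scoring and missing-data rules belong in an SAP, which may exist.** This is largely fair: the choice between ranks and means could be made there. But the definition in seconds, the 72-hour time point and what is recorded at the bedside are protocol matters. If nobody notes whether a patient was unable, declined or had gone home, no later plan can tell these apart.

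**The protocol does not prescribe a completers-only comparison of means.** This stands. Section 3 lets the data guide the test, and neither a rank test nor a comparison of proportions able is excluded. Seconds among those with a value is the natural reading, not a fixed plan.

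**A reader might infer that missing tests shrink any real effect.** The documents do not support that. They say nothing about how inability or discharge relates to TUG or to arm. The working shows that the bias can be nil, and that loss confined to one arm can inflate the gap.

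**A reader might also infer that the slowest and the fastest are lost at every time point, or that a discharged patient has no 72-hour value.** Neither is established. With a 48-hour infusion, discharge bears mainly on 72 hours and inability mainly on 24. The protocol does not rule out assessment after discharge; it only fails to describe it. The emphasis on early discharge in section 1.2 is general background, not local data, and section 2.3 expects mobilisation on the day of surgery.

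**Ranking does not rescue a small trial.** For a 15% difference and 30 per arm, power stays near 0.17. That is true. The case for ranking is that it keeps every patient who was assessed or unable, not that it makes TUG well powered.

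**Conclusion.** The point holds in a limited form. TUG is undefined for patients unable to do it, and the protocol describes no provision for those discharged before the 72-hour test. A comparison of seconds among completers selects on a post-randomisation state linked to the outcome. The bias is probably toward no difference, because the likeliest mechanism is that poor function causes inability in both arms alike, but direction and size cannot be known from the documents.

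The 64% and 35% losses assume log-normal times, a 15% effect and a sharp cut-off common to both arms. They lie at the severe end of the range for the strength of the link and should not be read as estimates for this trial. TUG is one of several secondary outcomes, so the primary conclusion on opioid consumption is untouched. The change is worth making before enrolment because the reason for a missing test is hard to recover later.

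**What to change.** - **Record.** At 24, 48 and 72 hours, note whether TUG was done and, if not, why: unable because of pain, weakness or dizziness; refused; or discharged.
- **24 and 48 hours.** Give unable patients the worst rank, compare arms by rank-sum, and report the number able to complete in each arm.
- **72 hours.** Either state how TUG and knee flexion are obtained after discharge, or present both as descriptive, with the number discharged in each arm.

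Two alternatives for discharged patients are tempting but weak. Giving them the best rank treats discharge as proof of walking ability and builds length of stay into TUG. Carrying forward an earlier TUG assigns a time that is probably too slow to patients who are still improving.

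The cost is one field on the form and a few sentences in the protocol. The downside is that the result is a rank shift and not a difference in seconds; seconds among completers can still be shown descriptively.
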